### 15.4 Sample Size

Based on preliminary data on these therapies, we expect to require 15 patients for the Phase Ib portion of the trial. However, with 4 dose levels it is possible, though not likely that 24 patients will be required. For the phase II portion of the trial, we will require  $17+6=23$  to  $37+12=49$  (23-59) patients depending on whether the number of responses reach the threshold at the interim analysis. Patients in the phase I portion who are the recommended dose for phase II will be included in the evaluable patients for phase II. The total sample size for the study will be approximately 73 patients.

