#### *Phase II*

- To evaluate the efficacy, as measured by clinical benefit rate (CBR), of enzalutamide + taselisib in patients with AR+ TN MBC. CBR is defined as the proportion of patients with a best response of CR, PR, or stable disease (SD)  $\geq 16$  weeks.

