### 2.2 Secondary Objectives

- To determine the progression free survival (PFS) of enzalutamide + taselisib in patients with AR+ TN MBC. PFS is defined as the time from cycle 1, day 1 until objective tumor progression.
- To assess the pharmacokinetics (PKs) of taselisib and enzalutamide in patients with AR+ TN MBC

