## 4. PARTICIPANT SELECTION

### 4.1 Inclusion criteria

- 4.1.1 Patients must provide informed written consent.
- 4.1.2 Patients must be  $\geq 18$  years of age.
- 4.1.3 ECOG performance status 0-1.
- 4.1.4 Clinical stage IV invasive mammary carcinoma
- 4.1.5 For phase 1b: HER2 negative, as defined for phase II. Any ER/PR (negative or positive) can be enrolled in the phase 1b portion. For phase II: ER negative (defined as expression of ER in  $\leq 5\%$  cells), PR negative (defined as expression of PR in  $\leq 5\%$  cells), HER2 negative [acceptable methods of HER2 analysis include IHC (0, 1+), fluorescence in situ hybridization (FISH) with HER2/CEN-17 ratio  $< 2$ , and/or chromogenic in situ hybridization (CISH) with HER2/CEN-17 ratio  $< 2$ ], as previously documented by histological analysis.
- 4.1.6 Androgen receptor positivity, defined as  $\geq 10\%$  of tumor cell nuclei with immunoreactivity for AR on central review at Vanderbilt.

- 4.1.7** Measurable or evaluable disease. Measurable disease is defined as at least one lesion that can be accurately measured in at least one dimension by RECIST criteria 1.1, with radiologic scans within 28 days of day 1, cycle 1. Evaluable disease must include bone metastases (pleural effusions and ascites are not considered evaluable for this study).
- 4.1.8** Any number of prior therapies as long as patients have adequate performance status and meet all other eligibility criteria.
- 4.1.9** Prior treatment with anti-androgens other than enzalutamide is acceptable.
- 4.1.10** Phase 1b only: FFPB or fresh frozen tissue from the original diagnosis or the metastatic setting should be located. Tissue must be submitted with 3 weeks of study initiation.

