### 6.2 Phase Ib component of the trial

The phase Ib component is complete. The primary objective of this portion of the trial was to determine the safety profile [dose-limiting toxicities (DLTs) during the first cycle of treatment, and maximum tolerated dose (MTD)] of the combination of taselisib and enzalutamide. The phase Ib portion allowed patients who are estrogen and/or progesterone receptor positive or negative, provided they are HER2 negative (see eligibility criterion 4.1.5).

- Enzalutamide + taselisib: the taselisib dose will start at 2 mg (dose level 1). Dose escalation proceeded among cohorts of 3 patients according to a standard 3+3 algorithm beginning at the lowest dose level.

In addition, pharmacokinetic (PK) sampling was collected from patients enrolled into the Phase Ib part of the study to allow for comparison within the study and to previous observations when taselisib was administered as a single agent in the Phase Ia trials. All open sites were able to participate in the phase Ib component.

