### 6.2.2 Definition of Dose-Limiting Toxicity (DLT)

Any of the following events that occur during Cycle 1 (first 4 weeks) was considered a DLT when possibly, probably or definitively classified as drug-related (according to NCI CTCAE v 4.0 Requirements). Whenever a patient experienced toxicity that fulfilled the criteria for a DLT, treatment with taselisib was held and the toxicity was followed up, Dose reductions as listed in Section 7.1 were followed. No DLTs were noted in the phase Ib.

Toxicity	DLT criteria	Follow-Up Evaluation
Hematologic	
 
Anemia CTCAE Grade <math>\geq 3</math> will not be considered a DLT unless judged to be a hemolytic process secondary to study drug.
 
Febrile neutropenia CTCAE Grade <math>\geq 3</math>
 
ANC CTCAE Grade 3 for <math>> 7</math> consecutive days. G-CSF use is permitted during the DLT window.
 
ANC CTCAE Grade 4
 
Platelet count CTCAE Grade 3 for <math>> 7</math> consecutive days and/or with signs of excessive bleeding
 
Platelet count CTCAE Grade 4
 
	
If <math>\geq</math> CTCAE grade 3 neutropenia or <math>\geq</math> CTCAE grade 3 thrombocytopenia have been demonstrated, these parameters must be repeated at least once a week until resolution to <math>\leq</math> CTCAE grade 1 neutropenia or <math>\leq</math> CTCAE grade 1 thrombocytopenia to allow for initiation of re-treatment, and then at least weekly until either resolution or until stabilization.

Table 1: DLT criteria and Follow-up Evaluation (CTCAE v 4.0)		
Toxicity	DLT criteria	Follow-Up Evaluation

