### 6.2.3 Definition of Maximum Tolerated Dose (MTD)

The MTD was defined as the highest dose of taselisib tested in which a DLT is experienced by 0-1 out of 6 patients among the dose levels. The dose of enzalutamide remained constant. The first cohort of patients (3 patients) in each arm started at dose level 1, and each patient was observed for 4 weeks on the specified dose and instructions were followed as below:

- If no patient in the first cohort of 3 experiences a DLT, dose escalation will proceed and patients will be accrued at the next dose level. If 1 of these patients experiences a DLT, the cohort will be expanded to 6 patients. If <33% of these patients experiences a DLT (e.g., 1 of 6 patients), dose escalation may proceed.
- If a DLT is observed in  $\geq 33\%$  of the patients in a given cohort (e.g.  $\geq 2$  of 6 patients), the MTD will have been exceeded and the lower dose level will be evaluated.

An exception to the above rule would be in the case in which the two DLTs observed out of 6 patients are both hematologic in nature and potentially reflect poor bone marrow reserve in this heterogeneous patient population and not the true MTD for the combination. In this instance, up to 3 additional patients may be enrolled to expand the total cohort size to 9 patients to assess for further DLT. In this situation, if a third DLT is observed, the MTD will have been exceeded and the lower dose level will be evaluated.

- If the 2 mg dose does not exceed the MTD, then dose escalation will proceed to the 4 mg dose. If the 4 mg dose does not exceed the MTD, then dose escalation will proceed to the 6 mg dose, and if the 6 mg dose does not exceed the MTD, then dose escalation will proceed to the 8 mg dose. If <33% of patients experience a DLT in the 8 mg cohort, then this dose level will be the maximum administered dose (MAD).

No new cohort of patients will be treated until the previous cohort has been fully evaluated for toxicity. Patients requiring dose reduction for reasons other than a DLT in cycle 1 of the phase Ib portion will not be included in the DLT evaluation. If the frequency of Grade 3 or 4 toxicities or other unacceptable lower grade chronic toxicities in the phase 1b portion suggests that the MTD has been exceeded at that dose level, any remaining accrual at that dose level will be halted and a lower dose of taselisib may be examined.

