## 6.3 Phase II component of the trial

Based on the phase Ib and data from other studies of taselisib, the recommended dose of taselisib for phase II is 4 mg. Note that dose reduction within patients (individually) is allowed. Dose reduction will be required for a given patient in case of grade 3 or 4 toxicities.

The primary efficacy endpoint is clinical benefit rate (CBR) of enzalutamide + taselisib in patients with androgen receptor positive triple negative metastatic breast cancer. Secondary objectives are to determine the ORR and progression free survival (PFS). CBR is defined as the proportion of patients achieving a complete response (CR) plus partial response (PR) plus stable disease (SD)

for at least 16 weeks. To assess objective responses, we will estimate the overall tumor burden at baseline to which subsequent measurements [performed every 2 cycles using the Solid Tumor Response Criteria (RECIST) v1.1] will be compared.

Section 6.3.1 and 6.3.2 discuss administration of taselisib and enzalutamide. Patients on the combination arm can take both drugs at the same time. Patients on the enzalutamide only arm should take enzalutamide only as directed below.

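### Section 15.4 carries phase Ib patients into the phase II evaluable set on dose alone, so patients who fail the phase II ER/PR criterion could count in the triple-negative CBR decision

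*Combined protocol and SAP*

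**What the plan says.** **Carry-over rule.** Section 15.4: "Patients in the phase I portion who are the recommended dose for phase II will be included in the evaluable patients for phase II". The sentence sets no ER/PR condition.

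**Who entered phase Ib.** Section 4.1.5: "Any ER/PR (negative or positive) can be enrolled in the phase 1b portion". Section 6.2, which describes phase Ib as complete, confirms it: "The phase Ib portion allowed patients who are estrogen and/or progesterone receptor positive or negative". AR positivity and HER2 negativity were required in both phases, so ER/PR status is the only receptor criterion that differs. For phase II, 4.1.5 requires ER and PR each in at most 5% of cells.

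**Target population.** The phase II primary objective (2.1) is "To evaluate the efficacy, as measured by clinical benefit rate (CBR), of enzalutamide + taselisib in patients with AR+ TN MBC". Section 6.3 agrees: "The primary efficacy endpoint is clinical benefit rate (CBR) of enzalutamide + taselisib in patients with androgen receptor positive triple negative metastatic breast cancer". Section 15.1 describes the trial population in the same terms. The PFS objective (2.2) is "To determine the progression free survival (PFS) of enzalutamide + taselisib in patients with AR+ TN MBC".

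**Decision rule.** Section 15.3 sets a Simon optimal two-stage design on the combination arm. It tests a CBR of 20% against 40%, stops at 3 or fewer of 17, and declares the regimen worthy at 11 or more of 37. It draws the first 17 from the phase II portion.

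**Analysis sets.** Section 15.5 takes everyone with at least four weeks of drug. Section 15.7 takes eligible patients with four weeks of drug for the main CBR analysis and does not name the phase whose criteria apply. Section 15.6 defines the ORR and PFS sets by dose.

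**The concern.** The decision rule is calibrated for one population, but the sentence that fills the evaluable set selects on dose. An ER/PR-positive patient treated at 4 mg in phase Ib satisfied 4.1.5 as written for phase Ib, so the eligibility condition in 15.7 does not clearly remove that patient from the main CBR set.

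The carry-over set is probably not empty. The recommended phase II dose is 4 mg (6.3), which was phase Ib dose level 2 (6.2.1). Section 7.2.1.3 reports that phase Ib escalated to 8 mg, so it should have passed through 4 mg.

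If such patients benefit more often than triple-negative patients do, the regimen can be declared worthy too easily. If they benefit less often, power falls. Whether they count at the interim look is also unclear: 15.3 refers to the phase II portion, while 15.4 makes carried-over patients evaluable for phase II. Two analysts could follow the plan in good faith and reach different counts against the same threshold.

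**Working it through.** **Inputs from the documents.** n1 = 17, stop at 3 or fewer; n = 37, worthy at 11 or more; null 20%, alternative 40%; stated early stopping under the null 55% (all 15.3).

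**Assumed inputs.** k = number of ER/PR-positive phase Ib patients at 4 mg, all counted inside the 37; q = their CBR. Neither is in the documents. I take k = 1 to 3. Section 6.2.2 says "No DLTs were noted in the phase Ib" and 6.2.3 says "If no patient in the first cohort of 3 experiences a DLT, dose escalation will proceed", which makes three the rule-based cohort size at 4 mg. It is not a reported count.

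**Step 1: reproduce the plan.** With X1 ~ Bin(17, p) and X2 ~ Bin(20, p):

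- Early stopping at p = 0.20: P(X1 ≤ 3) = 0.0225 + 0.0957 + 0.1914 + 0.2393 = 0.549, matching the stated 55%.
- P(worthy) = Σ over x = 4 to 17 of P(X1 = x) · P(X2 ≥ 11 − x). At p = 0.20 this is 0.0948 (type I error); at p = 0.40 it is 0.9033 (power).

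The design figures are correct. The question is who fills the 17 and the 37.

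**Step 2: put k patients with CBR q into the same rule.**

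- Counted only in the final 37: X1 ~ Bin(17, p); X2 ~ Bin(k, q) + Bin(20 − k, p).
- Counted in stage 1: X1 ~ Bin(k, q) + Bin(17 − k, p); X2 ~ Bin(20, p).

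Boundaries are unchanged.

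Type I error, triple-negative CBR 20% (final only / stage 1):

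| q | k = 1 | k = 2 | k = 3 |
|---|---|---|---|
| 10% | 0.088 / 0.087 | 0.082 / 0.079 | 0.076 / 0.072 |
| 20% | 0.095 / 0.095 | 0.095 / 0.095 | 0.095 / 0.095 |
| 30% | 0.101 / 0.103 | 0.108 / 0.111 | 0.115 / 0.120 |
| 50% | 0.114 / 0.119 | 0.135 / 0.147 | 0.158 / 0.179 |

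Early stopping under the null with k = 3 in stage 1: 0.623 at q = 10%, 0.476 at 30% and 0.335 at 50%, against 0.549 as designed.

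Power, triple-negative CBR 40%, k = 3 (final only / stage 1): 0.863 / 0.828 at q = 10%; 0.878 / 0.856 at 20%; 0.903 / 0.903 at 40%; 0.914 / 0.923 at 50%.

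**Step 3: a larger count.** If the cohort had been six, all ER/PR-positive, type I error (final only / stage 1) would be 0.060 / 0.052 at q = 10% and 0.183 / 0.216 at q = 40%.

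**The case against.** The strongest reply is that the population is already fixed elsewhere. Sections 2.1, 2.2, 6.3 and 15.1 and the phase II part of 4.1.5 all say triple negative, and for a phase II endpoint the natural reading of eligibility in 15.7 is phase II eligibility. On this view 15.4 is a loosely worded sample-size remark about dose. Section 15.5 shows how loose the section is: read literally, it would bring monotherapy patients and other phase Ib dose levels into the efficacy evaluation.

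Much of this is fair as evidence of intent, and pooling ER/PR-positive patients may well not be intended. But 15.4 is the only sentence that says what happens to phase Ib patients in phase II, and nothing states which phase's ER/PR criterion governs them.

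Other points that stand, without removing the gap:

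- Section 15.3 describes the source of the 20% null only as a study in a similar patient population.
- Sections 15.3 and 15.4 can be reconciled if carried-over patients count only in the final 37. That makes the stage 1 figures the less supported scenario, but the plan does not say so.
- Three is not a proven ceiling. Section 15.4 expects 15 phase Ib patients over four levels, more than 4 × 3 = 12.
- The ORR and PFS analyses carry no decision rule, so the mismatch in 15.6 is secondary.

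**Conclusion.** The concern holds. The plan's stated rule admits phase Ib patients to the phase II evaluable set on dose alone, and no other section rules out those who fail the phase II ER/PR criterion. Confidence is high for this gap in the text.

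The numerical consequence is conditional on an assumed count and an assumed CBR. It takes little to cross the design's 10% limit: one such patient with a CBR of 30% brings type I error to 10.1% (final only) or 10.3% (stage 1). A CBR below the triple-negative rate moves type I error and power down instead. The effect is zero if all carried-over patients were triple negative. This should be fixed, because the primary analysis set must be unambiguous before the 11-of-37 rule is applied.

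**What to change.** - **15.4:** limit carry-over to phase Ib patients at the recommended dose who meet the phase II ER/PR/HER2 definition in 4.1.5. State that they count inside the 37, and whether they count in the first 17.
- **15.3:** match the stage 1 wording to that choice.
- **15.7:** state that the phase II eligibility criteria define the main CBR set.
- **15.6:** use the same set for ORR and PFS. Report other phase Ib patients at that dose separately.

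**Cost.** One clause in 15.4 and short matching text in three sections; no boundary changes. Any ER/PR-positive phase Ib patient already counted must be replaced, not simply dropped: removing three from stage 1 without replacement (14 then 34 patients, same boundaries) would give type I error 0.051 and power 0.798. Replacement fits the stated numbers: 37 + 12 = 49 for phase II, and 49 + 24 = 73, the stated total, so no deduction was taken for carry-over.

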The following were instructions for DLTs in the phase Ib. Patients who meet DLT criteria must stop taselisib. Patients who meet DLT criteria for hepatotoxicity should hold both taselisib and enzalutamide. Patients whose treatment is interrupted or permanently discontinued due to an adverse event or clinically significant laboratory value must be followed as outlined in the table above, at least once a week for 4 weeks, and subsequently at 4-week intervals, until resolution or stabilization of the event, whichever comes first. Patients that require a dose delay of  $> 28$  days due to a cause unrelated to study participation will have the opportunity to continue study if deemed appropriate to do so by the Protocol Chair of the study. If patients experience a DLT considered related to taselisib, the patient may remain on enzalutamide on-study after resolution of the DLT at the discretion of the treating physician after receiving counseling about alternate treatment options. If patients experience a DLT considered related to enzalutamide, they have the option of remaining on single agent GDC0032 on-study at the discretion of the treating physician after receiving counseling about alternative treatment options. After resolution of the DLT, patients may be able to restart taselisib or enzalutamide at a lower dose at the discretion of the treating physician. However, such cases will be considered a DLT for the purposes of defining the MTD. All patients who continue taking taselisib and/or enzalutamide as a single agent will not be evaluable.

Patients who withdraw or are withdrawn from the study prior to completing the DLT assessment window for any reason other than a DLT or miss  $\geq 7$  days for non-drug related AEs will be replaced. This includes patients whose disease progresses within 30 days of starting the study. Patients requiring dose reduction of enzalutamide or taselisib for reasons other than a DLT in cycle 1 of the phase Ib portion will not be included in the DLT evaluation. After the MTD is reached,

patients in the phase Ib on lower dose levels can dose escalate to the MTD at the discretion of the treating physician and after discussion with the Protocol Chair.

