### 15.3 Phase II Study

The primary endpoint of the phase II portion is to assess the CBR of enzalutamide + taselisib at 16 weeks. This will be studied using a Simon two-stage design. Because there is sparse data on single agent enzalutamide, we also plan to accrue patients to a single agent enzalutamide arm. Patients will be randomized to the dual therapy vs monotherapy arms using a 3:1 randomization. The coordinating center (VICC) will randomly assign patients to an arm. No direct comparison of the two arms will be conducted. Rather, the monotherapy arm will serve as an informal anchor when interpreting results, and will be especially informative when interpreting many of the secondary analyses.

We have designed the enzalutamide + taselisib arm as a Simon optimal two stage. This design allows for early termination for inefficacy. The antiandrogen bicalutamide, in a prior study with a similar patient population, resulted a CBR of approximately 20%. Thus, for this study, we aim to show an improvement in CBR from 20% to 40%. With a Type I error of 10% and a Type II error of 10%, we will accrue 17 patients in the first stage. After the first 17 patients in the phase II portion have completed 2 cycles and obtained scans, the data will be analyzed. If 4 out of the 17 have a response (CR, PR, or SD), we will expand the study to a total of 37. If, at the end of the trial, there are 11 out of 37 patients with response, we will deem the regimen worthy of further study. If there are 3 or few responses in the first 17 patients, the study will terminate early. If 10 or few responses are seen in the total of 37, the regimen will be deemed unworthy of further study. This study has a 55% probability of stopping early under the null hypothesis. Patients whose disease progresses within 30 days of starting the study without a DLT will be replaced during the phase I portion.

Concurrently, an arm of single agent enzalutimide will be accrued. For every 3 patients randomized to the enzalutamide + taselisib arm, 1 patient will be randomized to the enzalutamide only arm. If the dual therapy arm terminates early due to inefficacy, we will also terminate the monotherapy arm. Thus, this arm will have a minimum of 6 and a maximum of 12 patients. We do not plan to do any formal analysis on this group of patients.

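### Section 15.4 carries phase Ib patients into the phase II count, so the Simon rule's 10% type I error rests on undocumented assumptions instead of holding by design

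*Combined protocol and SAP*

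**What the plan says.** Section 15.3 sets a Simon optimal two-stage design for the combination arm, with a null clinical benefit rate (CBR) of 20% and a target of 40%: "With a Type I error of 10% and a Type II error of 10%, we will accrue 17 patients in the first stage". The futility rule is "If there are 3 or few responses in the first 17 patients, the study will terminate early". The regimen also fails with 10 or fewer responses among 37. The section states a 55% chance of stopping early under the null. On who is counted, it says "After the first 17 patients in the phase II portion have completed 2 cycles and obtained scans, the data will be analyzed".

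Section 15.4 then adds: "Patients in the phase I portion who are the recommended dose for phase II will be included in the evaluable patients for phase II". I read this as patients treated at that dose. It does not say whether starting or current dose is meant, or whether these patients take places among the 17 and 37.

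On the dose, section 15.2 has phase II start at the MTD. Section 6.2.2 reports no DLTs in phase Ib, and section 7.2.1.3 says escalation reached 8 mg. Section 6.3 states: "Based on the phase Ib and data from other studies of taselisib, the recommended dose of taselisib for phase II is 4 mg".

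On phase Ib conduct, section 15.3 says: "Patients whose disease progresses within 30 days of starting the study without a DLT will be replaced during the phase I portion". Section 7.2.1.3 records that the study was later amended so that all patients take enzalutamide alone for 28 days before taselisib.

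**The concern.** The 3/17 and 10/37 limits give their stated error rates only if each counted patient has a 20% chance of success under the null and the counted set was fixed without regard to outcome. The carry-in sentence puts both conditions in doubt. The added cohort is identified by a dose that was picked once phase Ib data existed, by a judgement outside the 3+3 rule. Its patients were recruited under a rule that replaced early progressors, and they were treated without the enzalutamide lead-in. If either condition fails in the favourable direction, an inactive regimen passes the futility look and the final rule more often than planned. Separately, a go/no-go rule cannot be applied cleanly while two sections describe its denominator differently.

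**Working it through.** **Inputs.** From section 15.3: p0 = 0.20, p1 = 0.40, n1 = 17, r1 = 3, n = 37, r = 10. From sections 6.2 and 6.2.1: four dose levels, with cohorts of 3 expandable to 6. The number treated at 4 mg is not given, so I take m = 3 (what 3+3 yields with no DLTs) and m = 6 as assumptions.

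**Step 1: reproduce the plan.** Early stop = P(X ≤ 3), X ~ Bin(17, p). Pass = sum over x > 3 of P(X = x) × P(Bin(20, p) > 10 − x).
- p = 0.20: early stop 54.9%, pass 9.48%.
- p = 0.40: pass 90.3%.

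The stated 10%, 10% and 55% are correct for 37 unselected patients.

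**Step 2: carry in m patients with k successes.** They are placed in stage 1 and the limits are kept. Pass given k = sum over x ~ Bin(17 − m, 0.2) with x + k > 3 of P(Bin(20, 0.2) > 10 − x − k). For m = 3 and k = 0, 1, 2, 3 this gives 0.0511, 0.1157, 0.2215, 0.3660. These are conditional chances, not type I error rates; they are needed only for averaging below.

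**Step 3: no selection.** Bin(3, 0.2) weights are 0.512, 0.384, 0.096, 0.008. The average is 0.0262 + 0.0444 + 0.0213 + 0.0029 = 0.0948. With m = 6 the average is also 0.0948. Pooling by itself leaves the error rate unchanged.

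**Step 4: hypothetical bound, where the carried-in cohort is the best responder of c cohorts.** The weights come from the cumulative probabilities 0.512, 0.896, 0.992, 1 raised to the power c.
- c = 2, m = 3: weights 0.2621, 0.5407, 0.1812, 0.0159; type I error 12.2%, early stop 46.2%.
- c = 4, m = 3: weights 0.0687, 0.5758, 0.3239, 0.0316; type I error 15.3%, early stop 37.1%.
- c = 4, m = 6: type I error 18.2%, early stop 29.1%.

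**Step 5: replacement alone.** If a fraction e progress within 30 days and are dropped, the carried-in null rate is 0.20/(1 − e). The documents give no e, so I assume 10% to 30%, giving rates of 0.222 to 0.286. I also assume no matching exclusion in phase II. Type I error is then 10.0% to 11.7% (m = 3) or 10.6% to 14.1% (m = 6).

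**Step 6: what could have been seen when 4 mg was chosen.** The 4 mg dose is level 2, and section 6.2.3 requires each cohort to be fully evaluated before the next starts. If the choice followed completion of level 4, at least 4 + 4 + 4 = 12 weeks had passed since the last 4 mg patient started. The first scan, after two 28-day cycles (8 weeks), could be known. It matters because section 15.3 reads stage 1 (CR, PR or SD) from scans after 2 cycles. The 16-week CBR need not have been known.

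**The case against.** A reader might infer that outcomes were known before the dose was chosen and that the 10% is therefore lost. The documents do not support that. Knowing outcomes does not change the error rate unless the dose choice, or the decision to pool, depended on response (step 3). Phase Ib was a safety study. Section 15.2 speaks of analysing safety data at its end, and section 6.2.3 allows a lower dose to be examined for chronic lower-grade toxicity. A choice of 4 mg on safety grounds is entirely plausible. This stands, and it is why step 4 is only a bound.

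A reader might also quote 22.2% or 36.6% from step 2 as inflated error rates. They assume a favourable count; with no success among 3 the figure is 5.1%, and together they average 9.5%.

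A third tempting argument uses section 6.2.2, where "patients in the phase Ib on lower dose levels can dose escalate to the MTD at the discretion of the treating physician": long-surviving 2 mg patients would join the count as known successes. This fails. With no DLTs and escalation to 8 mg, the MTD rule points to 8 mg, so such patients would not be at 4 mg.

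On replacement, sections 15.5 and 15.7 restrict the phase II efficacy analysis to patients treated for 4 weeks, which largely matches it. Sections 6.9 and 10.1.2 keep early failures in the response evaluation, so the match depends on which section governs. Nor do the documents say that replaced phase Ib patients leave the efficacy count.

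The lead-in difference is not confined to phase Ib either. Section 7.2.1.3 describes 8 combination-arm phase II patients with events that prompted the amendment.

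Finally, if the wording of section 15.3 governs, phase Ib patients are already excluded and only clarification is needed. Section 15.4 says otherwise, so that cannot be assumed.

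**Conclusion.** The concern holds in a limited form. The two sections do not agree on who is counted, and the stated 10% is not guaranteed once phase Ib patients are included. It remains 9.5% if the dose choice was independent of response and the carried-in patients share the 20% null; neither condition is documented. The 12.2% to 18.2% range measures exposure under response-driven selection, which the documents do not show. The 10.0% to 14.1% range for replacement rests on assumed early-progression rates and on no equivalent exclusion in phase II. I attach no figure to the lead-in difference. The number carried in (3 to 6) is an assumption throughout. This is worth correcting because the correction is cheap, not because the error rate is shown to be wrong. Nothing here bears on whether 4 mg is a suitable dose.

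**What to change.** In section 15.4, delete the carry-in sentence and state that the 17 and 37 are only patients randomised to enzalutamide + taselisib in phase II. Report phase Ib CBR, ORR and PFS separately and descriptively by assigned starting dose, including replaced patients. Apply the same restriction in section 15.6, where ORR and PFS are now defined by the recommended dose and not by study phase.

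With this change the 9.5% type I error, 90.3% power and 54.9% early stopping no longer depend on how the phase II dose was chosen. The cost is about 3 to 6 observations in the primary count. Enrolment does not grow: phase II needs 37 + 12 = 49, and 24 + 49 = 73 is the stated total, with nothing deducted for overlap.
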